### *Study for eligible subjects*

This crossover study has two treatment arms (placebo or Mifepristone 50 mg tablets every six hours) with each subject serving as her own control. After eligibility is confirmed, subjects will undergo baseline testing and will be randomized to one of the treatment arms. Testing will be performed before and at the end of seven days of treatment with the study agent. Study drug will be continued until completion of post-drug testing. Thus, subjects will take the study drug for a total of nine days during each treatment arm. There will be a washout period of at least six and no more than eight weeks after which subjects will be randomized to the other arm of the study with an identical testing schedule. Subjects will record any symptoms or adverse events on a calendar

throughout the study. Women will be asked to keep a record of any abnormal menstrual bleeding. Subjects will be asked not to start on any new diet or exercise regimen during the study and maintain a stable weight for at least 2 weeks prior to study entry.

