**Secondary Outcomes**

1. Change in fasting plasma glucose and insulin levels.
2. Change in area under the curve (AUC) insulin, AUCglucose/AUCinsulin, and insulin sensitivity index based on OGTT.
3. Change in pre- and post-prandial glucose levels.
4. Change in basal triglyceride level.
5. Change in free fatty clearance based on the effect of insulin on FFA in the FSIVGTT.
6. Change in HDL, LDL, and total cholesterol levels.
4. Change in weight, BMI, neck, waist and hip circumference. It is unlikely that these parameters will change with the short duration of administration, however.
5. Change in blood pressure. It is unlikely that these parameters will change with the short duration of administration, however.
6. Whole-body rate of regenerating cortisol (measured with 9,11,12,12-[(2)H(4)]cortisol tracer) will be analyzed in collaboration with [name]. On metabolism by dehydrogenation, d4F loses 11alpha- deuterium, forming trideuterated cortisone (d3E) and is regenerated by reduction to tri-deuterated cortisol (d3F). 11BHSD1 reductase activity can be measured specifically as conversion of d3E to d3F (40). The amount of regenerated cortisol at baseline will be assessed for correlation with basal measures of insulin sensitivity and triglyceride levels, and the change in these parameters in response to mifepristone.
7. Adverse events will be tallied and compared between treatments.

8. Change in total and free testosterone, androstenedione, DHEAS, ACTH and cortisol will be assessed between treatments as a measure of mifepristone effect.
9. Change in 5 alpha and beta-reduced cortisol metabolites, cortisol, cortisone and their tetra-hydro metabolites will be assessed between treatments.
10. Correlation between post-treatment mifepristone level and the change in triglyceride levels and insulin sensitivity in response to mifepristone.

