Based on current evidence, a compensatory rise in ACTH levels has been seen with mifepristone in healthy individuals at doses as low as 100 mg/day (when used as a single dose over 3 months) and 200 mg/day over 8 days (41 - 42). Given the uncertainty in the effect of the dose, we plan to do an interim analysis looking at the effect of the proposed dose (50 mg every 6 hours) on the HPA axis in the first 6 subjects (one randomization block). The data from the first 6 subjects will be unblinded to [name], the study statistician, only. If the 24 hour UFC value post mifepristone treatment is more than or equal to twice the upper limit of normal in four or more of the six subjects, then we will decrease the mifepristone dose to 25 mg every 6 hours (100 mg/day). However, if there is no significant increase in the levels (< twice the upper limit of normal), same dose of mifepristone will be continued throughout the study. If the mifepristone

dose is changed based on the results of the interim analysis, then the data from the first six subjects will not be used in the final analysis and 15 additional subjects will be enrolled prior to completion of the study. On the other hand, if no dose adjustment is required, the study analysis will be done as previously planned.

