9. *Hypokalemia* has been seen with the use of mifepristone in Cushing's syndrome. However, this is related to the significantly elevated cortisol levels seen in Cushing's syndrome which overwhelm the 11BHS2 enzyme leading to hypokalemia via its action at the mineralocorticoid receptor. Even if a compensatory rise in ACTH and cortisol level is seen with the low dose of mifepristone being used in this study, we do not anticipate the cortisol levels to go high enough to cause hypokalemia. However, a comprehensive metabolic panel that will include a potassium level will be checked both at the post-treatment visit (after 7 days of treatment with drug) as well as at the time of the safety visit (1 week after discontinuation of the study drug).
10. *MRI* uses a strong magnetic field and radiowaves instead of x-rays and therefore does not have any associated risk of radiation exposure. Patients are at risk for injury from the MRI magnet if they have pacemakers or other implanted electrical devices, dental implants, aneurysm clips (metal clips on the wall of a large artery), metallic prostheses (including metal pins and rods, heart valves and cochlear implants), implanted delivery pump or shrapnel fragments. All subjects will be screened for these conditions prior to the study. Women of child bearing potential will have a pregnancy test performed before the MRI. Gadolinium-based contrast agents may be used with the MRI study. Subjects will be screened for any history of allergic reactions to these agents prior to administration. MRI evaluations may cause claustrophobia. Should this occur the study will be stopped and re-scheduled with administration of a sedative if needed.

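### If the interim lowers the dose, the unqualified exclusion of the first six subjects also takes them out of the planned adverse-event comparison

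*Combined protocol and SAP*

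**What the plan says.** The interim paragraph of Study Analysis looks at the hypothalamic-pituitary-adrenal response in the first six subjects, who form one randomization block. The dose is halved, from 50 mg to 25 mg every six hours, if 24-hour urinary free cortisol (UFC) after mifepristone is "more than or equal to twice the upper limit of normal in four or more of the six subjects". In that case, "then the data from the first six subjects will not be used in the final analysis". Recruitment is then extended by 15 people. The exclusion does not say which data or which analyses it covers.

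Secondary Outcomes includes this item: "Adverse events will be tallied and compared between treatments". Neither Study Analysis nor any other section defines a safety population, a safety summary by dose, or an exception to the exclusion.

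Safety handling outside the final analysis is set out elsewhere:

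- **Subject Monitoring:** the safety monitoring board reviews laboratory results once ten patients have completed, and any unanticipated adverse events.
- **Adverse Events and Protocol Violations and Deviations:** serious adverse events go to the FDA within 10 days and non-serious ones annually. Unanticipated problems go to the IRB.
- **Risks/Discomforts, hypokalemia item:** potassium is measured after treatment and at the safety visit. It is not a listed outcome, nor is it among the variables named in Study Analysis.

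**The concern.** Leaving one dose out of a single-dose estimate of insulin sensitivity is reasonable, because the two doses need not have the same effect. That reason does not carry over to adverse events, where doses can be shown in separate columns. Each of the six who completes the crossover also has a placebo period of their own, so the within-subject comparison at the original dose remains valid.

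The exclusion is also not neutral with respect to safety. It operates only after a marked cortisol response in most of the block, and the subjects it removes had twice the daily dose of their replacements. If the rule is followed as written, the mifepristone-placebo comparison of adverse events loses that group. The Precis and Study Analysis both say that this pilot's data will be used to design a longer trial, so what the final report shows about tolerability by dose has some bearing on that work.

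**Working it through.** The plan gives no figure for the size of its safety comparison, so there is none to reproduce. The inputs are as follows.

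- Subjects excluded: 6. Additional subjects: 15. Both are from the interim paragraph of Study Analysis.
- Daily dose: 4 × 50 = 200 mg before a change and 4 × 25 = 100 mg after it (same paragraph).
- Days on drug: "subjects will take the study drug for a total of nine days during each treatment arm" (Study for eligible subjects).
- Assumed: no dropout, and nobody after the sixth subject begins at the original dose.

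**Share of exposed subjects removed.** 6 / (6 + 15) = 6/21 = 28.6%.

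**Share of cumulative mifepristone dose removed.** The six receive 6 × 9 × 200 = 10,800 mg. The fifteen receive 15 × 9 × 100 = 13,500 mg. The share is 10,800 / 24,300 = 44.4%.

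**Chance that the rule comes into force.** This is P(at least 4 of 6), binomial, with an assumed per-subject probability of reaching the UFC threshold:

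- 20%: 1.7%
- 50%: 34.4%
- 70%: 74.4%
- 90%: 98.4%

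The exclusion is therefore unlikely if few subjects respond and close to certain if nearly all do.

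**Chance that the comparison omits at least one event of a given type.** This is 1 − (1 − p)^6, where p is the per-subject risk at the original dose. The documents give no value for p, so a range is assumed:

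- p = 10%: 46.9%
- p = 20%: 73.8%
- p = 30%: 88.2%

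**Precision when no event is seen.** The one-sided 95% upper bound is 1 − 0.05^(1/n):

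- n = 21: 13.3%
- n = 15: 18.1%
- n = 6: 39.3%

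Comparing 13.3% with 18.1% supposes one event rate at both doses, which sits badly with an argument that dose matters. By dose, the fifteen at 100 mg/day give the same bound either way. For 200 mg/day the choice is between a weak bound of 39.3% from six subjects and, under the assumptions above, no information in the final analysis.

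**The case against.** The exclusion sentence names neither adverse events nor laboratory results. It belongs to an interim about hormone response, in a section mainly about metabolic outcomes, and the authors may have meant efficacy only. That reading is plausible, but nothing in the text states it. With adverse events listed as a compared outcome, the literal rule covers them. If efficacy was all that was meant, the fix simply records it.

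The rest of the case against limits how far the point reaches, and most of it stands. A reader might infer any of the following, and the documents support none of them:

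- **That the six subjects' safety data are lost to oversight.** FDA and IRB reporting do not depend on the final analysis set. The safety board's review after ten completers would ordinarily include those of the six who complete.
- **That a potassium comparison is lost.** None is planned. Potassium is a monitoring test and is affected only if the final report summarises safety laboratory results.
- **That these six would settle the hypokalemia question.** Risks/Discomforts says "we do not anticipate the cortisol levels to go high enough to cause hypokalemia", but this already allows for a compensatory rise and refers to the much higher levels of Cushing's syndrome. Nothing in the documents places twice the upper limit of normal UFC in that range, and six subjects test little.
- **That the final comparison would describe the lower dose only.** No enrolment pause is stated, and each subject's two periods are six to eight weeks apart. A seventh or later subject could start at the original dose before the decision, and the rule would not exclude that subject.
- **That the report would necessarily look more favourable.** That presumes what the six would show.

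The effect is also conditional on the trigger. The link to the longer trial is indirect, since Study Analysis describes that trial in terms of glucose, lipids, weight and blood pressure.

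**Conclusion.** The point holds for the final adverse-event comparison and the report built on it, and no further. If the dose is lowered, the exclusion as written removes 6 of 21 mifepristone-exposed subjects (29%) and 44% of cumulative dose. All six were at the higher dose, in the one scenario where at least four of them reached the UFC threshold. The 29% and 44% assume no dropout and no later starters at the original dose. The 47–88% chance of omitting at least one event rests on assumed risks of 10–30% and should be read only as an illustration.

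This is a modest defect with a cheap remedy. It is still worth correcting beforehand, because the rule is written for exactly this scenario, and deciding what to keep after the six subjects' results are known would be harder to defend.

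**What to change.** In the interim paragraph of Study Analysis, limit the exclusion to the efficacy and pharmacodynamic estimates. Then add a sentence to this effect: *every subject who took study drug remains in the adverse-event comparison and in any safety-laboratory summary, including potassium, tabulated by dose actually received alongside the subject's own placebo period, with an additional row for all doses combined.* Tabulating by dose received also covers any later subject who began at the original dose before the decision.

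The cost is that sentence and one more column in the safety table, which may look slightly less favourable. The dosing, the interim trigger, the visits and the number of subjects do not change.

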## PHARMACEUTICAL SAFETY AND RANDOMIZATION

Mifepristone (HRA 052015; INN Mifepristone) is a cortisol and progesterone analog with antiprogestin and antiglucocorticoid activity. Healthy subjects receiving long-term mifepristone administration showed antiglucocorticoid effects at a daily dose of 10 mg/kg, which is about 5 – 10 fold greater than that required to demonstrate antiprogestin effects (43). The agent effectively reverses the clinical and glucocorticoid-dependent biochemical features of Cushing's syndrome (30). The proposed doses in this protocol are about 2 – 3 mg/kg/d.

Mifepristone will be given under an active IND (113,698) sponsored by Laboratoire HRA-Pharma. Laboratoire HRA-Pharma, NICHD's cooperative research and development partner, will provide mifepristone compound. The Pharmaceutical Development Service will formulate the compound into 50 mg capsules. Mifepristone will be manufactured, controlled and released according to current GMP guidelines. A look-alike inert placebo will be formulated into capsules by the Pharmaceutical Development Service.

The Pharmaceutical Development Service will randomize subjects in blocks of 6 to receive the two treatments. The investigators will not be informed of the treatment group of any participant while she receives study compound unless there is an adverse event requiring "unblinding" of the treatment. At the interim analysis, the treatment arm assignment for the first 6 subjects will only be revealed to [name], the study statistician. The rest of the study investigators will remain blinded.

The 20% 9,11,12,12-[H]4-cortisol and 80% hydrocortisone solution will be given under an active IND (113,698) sponsored by HRA-Pharma. The deuterated cortisol will be purchased from Cambridge Isotope Laboratories, Inc ([name]; [contact]; WEB: [www.isotope.com](http://www.isotope.com)). The Pharmaceutical Development Service will perform sterility and pyrogenicity testing and will formulate the 20% 9,11,12,12-[H]4-cortisol and 80% hydrocortisone solution.

## EVALUATION OF BENEFITS AND RISKS/DISCOMFORTS

### Benefits

Subjects may benefit by receiving a physical examination, and laboratory testing. In addition this study will contribute to our understanding of the physiology pertaining to the HPA axis and metabolic syndrome.

### Risks/Discomforts

We believe that this study does not involve significant risk for the volunteer subjects. The risks are anticipated to be greater than minimal, with the 7 day course of mifepristone too brief to offer the prospect of direct benefit to subjects. The medical procedures include physical examination, non-invasive tests (eg UFC and saliva collection), venipuncture and study agents with minimal side

effects at doses being used in the study. The risk: benefit ratio is low. The intravenous glucose tolerance test can be associated with greater than minimal risk, but these risks will be mitigated as noted below.

1. *Adrenal insufficiency* can be associated with the use of mifepristone given its antiglucocorticoid action. In a previous subchronic study, Laue and colleagues found that 8 of 11 healthy volunteers receiving mifepristone 10mg/kg/day for 7- 14 days exhibited generalized exanthem and one developed signs and symptoms of adrenal insufficiency. In all cases symptoms resolved 5 - 6 days after discontinuation of mifepristone (44). In another study by Lambert et al, chronic daily treatment with 200 mg for months, mifepristone daily was associated with mild nausea and fatigue but no other signs and symptoms of adrenal insufficiency (45). However, given the short duration of administration and smaller doses of mifepristone being used in this study, these effects are unlikely. No adverse effects were reported after single or two-day doses of up to 400 mg in previous studies, or after 200 mg daily for 8 days (32, 33, 46). All subjects will be educated on the signs and symptoms of adrenal insufficiency and will be instructed to contact study personnel if they develop any such symptoms. Detailed history with regards to signs and symptoms of adrenal insufficiency will also be taken during the study visits.
2. *Hypoglycemia* is a risk associated with the frequently sampled intravenous glucose tolerance test after insulin administration. The dose of insulin will be calculated meticulously and the test will be performed in a strictly monitored setting, with frequent measurement of glucose and the ability to administer additional glucose should hypoglycemia occur. Also, we believe that the risk of hypoglycemia with anticipated improvement in glucose intolerance on study drug in subjects on a stable dose of metformin is minimal. Glucose levels will however be monitored at every follow-up visit during the study.
3. *Deuterated isotopes* used to evaluate cortisol and cortisone dynamics are not radioactive and are not expected to have adverse effects.
4. *Endometrial hyperplasia and vaginal bleeding* is a theoretical risk with long-term administration of mifepristone. However, given the short duration of drug administration in this study we do not anticipate this effect. Postmenopausal women will be screened for pre-existing endometrial hyperplasia by ultrasound and any abnormal vaginal bleeding during the study will be investigated. An MRI Pelvis will be performed if the transvaginal ultrasound is unable to provide an accurate measurement of the endometrial stripe. Subjects in whom a definite assessment of endometrial thickness cannot be made with either ultrasound or MRI (as may be the case in patients with multiple fibroids) will be followed closely for any abnormal vaginal bleeding and will undergo a repeat transvaginal ultrasound upon completion of the study.
5. *Phlebotomy* is associated with mild discomfort and the possibility of bruising. There is a small risk of fainting, bleeding, or of infection. These will be minimized by placing the patient in a seated or supine posture and by the use of clean technique.
6. *Time* involved in clinic visit and inpatient stay may be a discomfort. Every effort will be made to streamline the visits, and the amount of time required will be specified in the consent form as clearly as possible. Women will be allowed to go out on pass when no testing is scheduled.

7. *Anemia* is a possible risk of phlebotomy. The total blood withdrawal over a six week period will be 425 ml which is within the NIH guideline of 450 ml for adults or 7ml/kg/6 weeks in all subjects. Every effort will be made to minimize the amount of blood drawn.
8. *Termination of pregnancy* is possible with mifepristone. Only non-pregnant women will be enrolled in the study. A pregnancy test will be obtained for all women at the screening visit and prior to study drug initiation. Women will be counseled regarding the risk of termination of pregnancy associated with study drug intake and will be asked to use non-hormonal contraceptive methods if they are sexually active during the study and for one month after stopping the study medication.
9. *Hypokalemia* has been seen with the use of mifepristone in Cushing's syndrome. However, this is related to the significantly elevated cortisol levels seen in Cushing's syndrome which overwhelm the 11BHS2 enzyme leading to hypokalemia via its action at the mineralocorticoid receptor. Even if a compensatory rise in ACTH and cortisol level is seen with the low dose of mifepristone being used in this study, we do not anticipate the cortisol levels to go high enough to cause hypokalemia. However, a comprehensive metabolic panel that will include a potassium level will be checked both at the post-treatment visit (after 7 days of treatment with drug) as well as at the time of the safety visit (1 week after discontinuation of the study drug).
10. *MRI* uses a strong magnetic field and radiowaves instead of x-rays and therefore does not have any associated risk of radiation exposure. Patients are at risk for injury from the MRI magnet if they have pacemakers or other implanted electrical devices, dental implants, aneurysm clips (metal clips on the wall of a large artery), metallic prostheses (including metal pins and rods, heart valves and cochlear implants), implanted delivery pump or shrapnel fragments. All subjects will be screened for these conditions prior to the study. Women of child bearing potential will have a pregnancy test performed before the MRI. Gadolinium-based contrast agents may be used with the MRI study. Subjects will be screened for any history of allergic reactions to these agents prior to administration. MRI evaluations may cause claustrophobia. Should this occur the study will be stopped and re-scheduled with administration of a sedative if needed.

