## **Study protocol**

### *Screening*

[figure not shown]
Subjects will undergo evaluation at the Clinical Center for eligibility. This will include measurement of height, weight, waist circumference, blood pressure, and a detailed history and physical examination. Subjects will be screened for depression using the PHQ-9 questionnaire. If a subject is found to have severe depression or suicidal ideation, they will be seen by a psychiatrist at NIH on an emergent basis and further management will be guided by their recommendations. An electrocardiogram will be obtained to identify any subjects with QTc interval prolongation. Screening laboratory tests will include a serum pregnancy test for females, fasting plasma glucose, HgbA1c, OGTT (2 hour, after 75 g dextrose), comprehensive metabolic panel, CBC with differential, coagulation profile, midnight salivary cortisol, TSH, Free T4, FSH and LH levels. HIV 1&2 antibody and hepatitis C antibody levels will also be checked if on history taking the subject is found to have risk factors for HIV or Hepatitis C. A transvaginal ultrasound will be obtained to evaluate endometrial thickness in postmenopausal women (defined as amenorrhea for  $\geq 12$  months and an FSH level in the postmenopausal range) as well as those in the perimenopausal phase (amenorrhea for  $\geq 6$  months and FSH level in the postmenopausal range). An MRI Pelvis will be performed only if the transvaginal ultrasound is unable to provide an accurate measurement of the endometrial stripe. Subjects in whom a definite assessment of endometrial thickness cannot be obtained with either ultrasound or MRI (as may be the case in patients with multiple fibroids) will be followed closely for any signs of abnormal vaginal bleeding and will undergo a repeat transvaginal ultrasound upon completion of the study.

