#### Day 10 – 12 (Wednesday-Friday):

After an overnight fast, all study procedures indicated for day 1 -3 will be repeated on day 10 - 12. Blood (5 ml) will be obtained on day 10 for measurement of post-treatment mifepristone level and to hold for other potential measurements related to cortisol metabolism. Subjects will continue on the study drug until the completion of all study procedures on day 12.

Day 19 and 33 (Friday): Safety monitoring

After discontinuation of study drug, subjects will return approximately one week (Day 19) and then 3 weeks (Day 33) after the last day of study drug intake for measurement of blood chemistries and CBC. The research team will make every effort to ensure that these safety follow-up visits are within 2 days of day 19 and day 33. However, for subject convenience, we will allow for the follow-up visits to be within 5 days of the expected date of follow-up (day 19 ± 5 days and day 33 ± 5 days). In these cases, a member of the study team will contact the study subject on the expected date of follow-up to ensure that the subject is doing well. If any potential treatment-related abnormalities/adverse events are noted at the safety visits, subjects will receive appropriate treatment for these abnormalities and will be followed closely as clinically indicated until the abnormalities/adverse events have fully resolved.

Second study treatment visit: These study procedures will be repeated with each study drug after a wash-out period of 6-8 weeks.

For subject convenience, we will allow for the pre-study drug testing (Days 1 through 3) in each treatment arm to be done on days other than as specified above as long as it is done no more than 10 days prior to study drug initiation.

Table 1: Schema for first admission testing. The second admission will be identical.

Sunday	Monday	Tuesday	Wednesday	Thursday	Friday	Saturday
Admit to 5SWN or 5NW	DAY 1 Fasting labs 24 hr urine  0900 Serial 24 h ACTH/Cortisol  Pre & post prandial glucose levels	DAY 2 0900 Complete serial ACTH/Cortisol  0930 Fasting lipids FSIVGTT  Can go out on pass	DAY 3 0800 3 hr OGTT  1800 START MIFEPRISTONE OR PLACEBO	DAY 4 On pass	DAY 5 On pass	DAY 6 On pass

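### Low priority: no pregnancy test is listed after the last dose of the second treatment; hCG at the existing Day 33 visit would close the gap cheaply

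*Combined protocol and SAP*

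**What the plan says.** **Tests listed.** Screening includes "a serum pregnancy test for females" (Screening). Item 8 of Risks/Discomforts, on termination of pregnancy, states: "A pregnancy test will be obtained for all women at the screening visit and prior to study drug initiation". Item 10 adds a test before any MRI. The pelvic MRI is itself part of screening, used only when ultrasound cannot measure the endometrium.

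**Second treatment.** After the washout, "subjects will be randomized to the other arm of the study with an identical testing schedule" (Study for eligible subjects).

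**After dosing.** The last dose in each treatment is on Day 12. Subjects return about one week later and then "3 weeks (Day 33) after the last day of study drug intake for measurement of blood chemistries and CBC", with allowed windows of "day 19 ± 5 days and day 33 ± 5 days" (Day 10 – 12, safety monitoring). Subject Monitoring likewise names a metabolic panel and a blood count. The later cortisol tracer visit is on clinical hold.

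**Other controls.** Women are counselled about the risk and "asked to use non-hormonal contraceptive methods if they are sexually active during the study and for one month after stopping the study medication" (Risks/Discomforts, item 8). They record abnormal menstrual bleeding, and under item 4 "any abnormal vaginal bleeding during the study will be investigated". Adverse events are sought by open questioning and calendar review. Pregnancy and abnormal vaginal bleeding are both withdrawal criteria.

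**The concern.** A negative test before the first dose cannot rule out a conception during the nine days of dosing that follow. In the first treatment, the pre-drug test of the second treatment acts as a later check. The second treatment has no successor, so its dosing period is the only one with no listed test after it. The named chemistries and blood count would not identify an early pregnancy.

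What is at stake is the care of one participant and a complete safety record. A rare exposed pregnancy could be recognised late, or not recorded at all, although the protocol itself names this risk. The primary outcome, the sample size and the analysis are not involved.

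**Working it through.** The plan gives no figure to reproduce on this point. The check sets out the schedule and then some day and rate arithmetic.

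**1. Pregnancy tests against dosing**

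| Point in the trial | Pregnancy test listed? |
|---|---|
| Screening | Yes |
| Before drug, first treatment | Yes |
| Days 19 and 33, first treatment | No |
| Before drug, second treatment | Yes, reading the pre-drug test as repeated under the identical schedule |
| Days 19 and 33, second treatment | No |

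Tests listed after the last dose of the second treatment: 0, in the text available. The consent pages and Figure 1 were not available.

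**2. Age of such a pregnancy at Day 33**

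- Last dose on Day 12, so a conception on or before it is at least 33 − 12 = 21 days old at Day 33.
- Earliest allowed visit: 33 − 5 = Day 28, giving 28 − 12 = 16 days.
- Assume a 28-day cycle with ovulation on cycle day 14, so that the next period is due 15 days after ovulation. Ovulation by Day 12 puts that period at Day 27 or earlier. It is then at least 33 − 27 = 6 days overdue at Day 33, or 28 − 27 = 1 day at the earliest visit.

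**3. Could ovulation fall within dosing?**

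Premenopausal women are tested on cycle days 1–7. If Day 1 falls on cycle day c, ovulation on cycle day 14 falls on study Day 15 − c.

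- c = 1 or 2: Day 14 or 13, after the last dose.
- c = 3 to 7: Day 12 to Day 8, within dosing (Day 3 evening to Day 12).

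So on the standard schedule it can fall on either side. The protocol also lets baseline testing be done up to 10 days before the drug starts, which shifts dosing later in the cycle.

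**4. Expected conceptions on mifepristone in the second treatment**

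From the protocol: 25 recruited (Study Analysis) and nine days of dosing. Assumed, because the documents give no figures: 10% to 40% of subjects are women of child-bearing potential, half take mifepristone second, and contraceptive failure is 5% to 20% per year.

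- Women of child-bearing potential: 25 × 0.10 = 2.5 to 25 × 0.40 = 10.
- Taking mifepristone second: 1.25 to 5.
- Risk spread evenly over the year: 1.25 × 0.05 × 9/365 = 0.0015, to 5 × 0.20 × 9/365 = 0.025.
- A whole cycle's risk falling in dosing (1/13 of the annual risk): 1.25 × 0.05/13 = 0.005, to 5 × 0.20/13 = 0.077.

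Overall range: about 0.002 to 0.08. With the 17 subjects of the pilot instead of 25, it is about 0.001 to 0.052.

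**5. Blood volume**

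Item 7 puts the six-week total at "425 ml which is within the NIH guideline of 450 ml for adults", and also cites a limit of 7 ml/kg over six weeks.

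- Headroom under the first limit: 450 − 425 = 25 ml. An assumed 5 ml tube would bring the total to 430 ml.
- Under the second limit, 430 ml requires a body weight of 430/7 = 61.4 kg. A woman of 1.55 m (assumption) at the lowest eligible BMI of 25 weighs 25 × 1.55² = 60.1 kg, so her limit is about 420 ml. That is already below the planned 425 ml.

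An extra tube therefore cannot be assumed to fit for every subject. Serum already drawn, or urine, avoids the question.

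**The case against.** The strongest case against is that this is a preference and corrects no error. The plan contradicts nothing here and breaks no commitment. It tests before dosing, counsels, asks for contraception, times testing to the cycle, keeps a calendar and investigates bleeding. By Day 33 an overdue period may already have raised the question, so the gain is confined to a woman whose overdue period goes unnoticed or unreported. All of that stands, and it is why the point is rated low.

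The test also misses part of the harm. The protocol says antiprogestin effects appear at far lower doses than antiglucocorticoid effects, so a conception during dosing might be lost early and hCG could be negative by Day 33. Such a loss would be expected to show as bleeding, which is already recorded and investigated. This stands too: the test mainly finds pregnancies that continue. No dose remains by then, so it prevents no exposure. A positive result could reflect a conception after dosing ended.

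The objection does not remove the gap for an ongoing pregnancy. Women are asked to record abnormal bleeding, and an absent period is not bleeding. Perimenopausal women with irregular cycles may be enrolled, and for them a late period says little.

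**Conclusion.** The gap is real but small. In the text available, the second dosing period is the only one with no pregnancy test listed after it, and a suitable visit with a blood draw already exists. The expected number of conceptions on mifepristone in that period is well under one, about 0.002 to 0.08. That range rests on the assumed share of women of child-bearing potential, the assumed contraceptive failure rate and an even split of sequences.

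Three stronger readings do not hold:

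- A reader might infer that the pregnancy risk is uncontrolled. Pre-dose tests, counselling and contraception address it.
- A reader might infer that neither treatment has a later check. The identical second schedule supports a test before the second drug, which also covers an ongoing pregnancy from the first.
- A reader might infer that a Day 33 test would show whether the drug had ended a pregnancy. It would not do so reliably.

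This is an optional safety improvement with no bearing on the trial's inference.

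**What to change.** For all women of child-bearing potential, add hCG at the Day 33 visit of the second treatment, on the serum already drawn for chemistries or on urine. Test everyone whatever their sequence, so that the test does not reveal who took mifepristone second. State that a positive result will be dated against the dosing days, followed up and recorded.

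Where possible, keep the visit close to Day 33. At Day 28 the margin past the expected period is only one day on the assumptions above. The test will not cover the full month of requested contraception: taking a month as 30 days, that runs to Day 12 + 30 = Day 42, nine days after the visit.

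The cost is one assay per woman, about 3 to 10 in the trial under the same 10% to 40% assumption. No visit is added and no blood is added against the 450 ml or 7 ml/kg limits. The documents give no assay price, so calling it cheap is a judgement.
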